7.1.1 Subject-specific Criteria for Discontinuation of Investigational Product

For any individual participant, further administration of IP will be stopped if any of the following scenarios occur:

- # Reports of drug-related SAE(s) or drug-related AE(s) including but not necessarily limited to:
 - Serious or severe drug-related injection site reactions
 - Anaphylactic reaction, defined as an immediately life-threatening allergic reaction with bronchoconstriction, angioedema, and/or hypotension (FDA 2014); or serious hypersensitivity reactions
 - Development of moderate-to-severe sensory abnormalities (eg, paraesthesia, dysesthesia, burning, pins and needles) that are not resolved within a 14-day period
 - Development of peripheral neuropathy
 - New onset of demyelinating disorder
 - Serious systemic infection
 - o Serious non-systemic infection if deemed necessary by the investigator

- # Any of the following are criteria for immediate and permanent discontinuation of IP (Section 8.2.11.1):
 - \circ ALT or AST > 5 × ULN for more than 2 weeks
 - ALT or AST ≥ 3 × ULN and coexisting total bilirubin ≥ 2 × ULN (Hy's Law [HL]). Hy's law is described in Section 8.3.8 and FU of HL cases is provided in Appendix F.
 - \circ ALT or AST \geq 3 × ULN and coexisting international normalised ratio (INR) > 1.5
 - ALT or AST ≥ 3 × ULN and associated with symptoms (which may be either transient or persistent) of hepatitis or hypersensitivity. Hepatitis symptoms include fatigue, nausea, vomiting, right upper quadrant pain or tenderness. Hypersensitivity symptoms include eosinophilia (≥ 5%), rash, or fever without clear alternative cause.
 - Any change in ALT or AST level (eg, < 3 × ULN) if there is a possibility of development of autoimmune hepatitis as per investigator's judgement. Participant should have a consult with a hepatologist, and liver chemistry values, as well as additional tests, should be completed as soon as possible (Appendix F 7)
- # AEs suggestive of autonomous nervous system dysfunction, including but not limited to confirmed orthostatic hypotension (Section 8.2.3.2) or significant bradycardia (Section 8.2.4) or syncope that after evaluation by a cardiologist (and/or neurologist) are considered to be a manifestation of sympathetic autonomic dysfunction
- # Cases when sympathetic neuropathy is not confirmed but orthostatic hypotension remains symptomatic for more than 14 days
- # Participants who have a proven diagnosis of sympathetic autonomic neuropathy
- # Development of malignancy
- # Development of Class 3 or Class 4 (NYHA 1994) heart failure
- # Positively-adjudicated possible or probable RPOA, SIF, primary osteonecrosis (including spontaneous osteonecrosis of the knee), or pathological fracture.
- # Participants who plan to undergo total joint replacement (knee, hip, or shoulder) or other arthroplasty procedure during the study
- # Haematologic toxicity, defined as one or more of the following:*
 - Leukocyte count $< 2.0 \times 10^9/L$
 - \circ Neutrophil count $< 1.0 \times 10^{9}/L$
 - \circ Platelet count < 75 × 10⁹/L
 - * Note: Participants must be advised to seek immediate medical attention if they develop any symptoms suggestive of blood dyscrasia or infection (eg,

persistent fever, sore throat, bruising, bleeding, or pallor). Haematology testing should be performed as soon as possible to exclude blood dyscrasia.

- # Development of a lupus-like syndrome, autoimmune hepatitis, or immune-complex disease
- # Development of COVID-19 infection that meets moderate or severe severity AE criteria.
- # Treatment with anti-SARS-CoV-2 monoclonal antibodies for COVID-19 infection of any severity.
- # Mild or asymptomatic COVID-19 infection with symptoms that have not resolved within 28 days since the last IP administration or results of appropriate testing for COVID-19 infection (ie, antigen-based) suggesting that a participant is carrying a replicating virus and remains positive within 28 days since the last IP administration.
- # There are other ongoing sequelae from COVID-19 infection, or the participant requires treatment for the manifestations of COVID-19 infection for the period beyond 28 days since the previous IP administration, or less than 5 half-lives have passed since the last COVID-19 antiviral medications administration within the 28-day period since the last IP administration.
- # If per investigator's judgement, the amount of rescue medication taken by the participant poses a risk for the participant to continue safely in the study.

7.1.2 **Procedures for Early Discontinuation of Investigational Product**

A participant who discontinues IP early (ie, prior to receiving the last dose of IP) should always be asked about the reason(s) and the presence of any AEs. The reason for premature discontinuation of IP should be documented in the source documentation and recorded in the eCRF.

Participants who discontinue IP early will be asked to complete study assessments at the ET visit (ie, Week 12 assessments) as soon as possible and then to enter the FU period.

Participants who discontinue IP prematurely may be given standard-of-care therapy for their pain after the ET visit as deemed appropriate by the investigator and in alignment with local guidelines/label (including paracetamol, aspirin, NSAIDs, and COX-2 inhibitors if deemed necessary). However, initiation of NSAIDs, COX-2 inhibitors, and aspirin (in doses that exceed 325 mg/day) is prohibited until after 5 half-lives following the last IP administration (ie, approximately 3 weeks). Note that it is recommended to postpone NSAIDs/COX-2 inhibitors intake until 8 weeks after the last IP administration. In addition, initiation of corticosteroid therapy (eg, intra-articular injections) should be deferred until at **least 8 weeks** after the last IP administration.

Refer to the SoA (Table 1) for assessments to be performed at the ET visit and FU period. All participants prematurely discontinued from IP are expected to complete the ET visit and the 24-week FU period, which consists of 3 FU clinic visits and 4 phone calls at the times indicated below:

- ∀ ET visit: Week 12 assessments to be performed as soon as possible after the last IP administration. The following assessments/procedures will not be performed beyond the ET visit:
 - # Daily NRS pain score
 - # DSIS
 - # Rescue medication recording
 - # WOMAC
 - # PGA
 - # Blood collection for PK, ADA, and PD biomarkers
- ∀ FU phone call 1: To be conducted 5 weeks after the last IP administration
- ∀ FU visit 1: Week 18 assessments to be performed 8 weeks after the last IP administration
- ∀ FU phone call 2: To be conducted 11 weeks after the last IP administration
- ∀ FU phone call 3: To be conducted 14 weeks after the after the last IP administration
- ∀ FU phone call 4: To be conducted 18 weeks after the last IP administration
- ∀ FU visit 2: Week 32 assessments to be performed 22 weeks after the last IP administration
- ∀ FU visit 3: Week 36 assessments to be performed 26 weeks after the last IP administration

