7 DISCONTINUATION OF STUDY INTERVENTION AND SUBJECT DISCONTINUATION/WITHDRAWAL

7.1 Discontinuation of Investigational Product

It may be necessary for a participant to permanently discontinue (definitive discontinuation) IP. Participants will discontinue IP in the following situations:

- ∀ Participant decision. The participant is at any time free to discontinue treatment, without prejudice to further treatment. Participants must be withdrawn from the study if they withdraw consent to participate. The participant should always be asked about the reason(s) and presence of any AEs.
- \forall AE that, in the opinion of the investigator, contraindicates further dosing
- \forall Serious noncompliance with the CSP
- ∀ Risk to participant as judged by the investigator or AstraZeneca
- ∀ If a study participant is vaccinated with a COVID-19 vaccine during the treatment period of the study, he/she should be discontinued from IP administration. The study participant will still be required to attend scheduled safety visits and to complete the follow-up period of the study (Refer to Section 7.1.2 for "Procedures for Early Discontinuation of Investigational Product"). If a study participant is vaccinated during the follow-up period, they should continue participation in the follow-up period of the study.
- \forall Development of any of the participant-specific criteria for discontinuation (Section 7.1.1)

The sponsor reserves the right to request the withdrawal of a participant due to protocol deviations or other reasons.

Participants will be asked to complete study assessments at the ET visit (ie, Week 12 assessments) as soon as possible and then to enter the FU period. Refer to the SoA (Table 1) for assessments to be performed at the ET visit and FU period and to Section 7.1.2 for procedures for early discontinuation of IP.

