7.1.3 Temporary Discontinuation of Investigational Product

Withholding IP administration temporarily may be considered in the following cases:

- ∀ Development of sensory abnormalities (eg, paraesthesia, dysesthesia, burning, pins and needles) to confirm their resolution within 14 days prior to the next IP administration
- ∀ AE suggestive of new occurrence or worsening of peripheral neuropathy
- ∀ Participants who have the following sympathetic function AEs (any seriousness or severity):
 - # Meet the prespecified criteria for bradycardia (Section 8.2.4)
 - # Meet the prespecified criteria for confirmed orthostatic hypotension (Section 8.2.3.2)
 - # Have syncope
 - # Report anhidrosis or hypohidrosis
- ∀ Cases where additional evaluation or adjudication is needed to exclude possible or probable RPOA, SIF, primary osteonecrosis (including spontaneous osteonecrosis of the knee), or pathological fracture.

- ∀ Cases of signs/symptoms suggestive of worsening or new occurrence of heart failure
- ∀ When follow-up on cases of abnormal liver function is needed before the decision on permanent IP discontinuation is made (eg, identification of potential HL (PHL) cases needed or further evaluation in order to exclude HL required, or ALT or AST ≥ 5 × ULN for less than 2 weeks)
- \forall A positive test for SARS-CoV-2 at any time point during participation in the study.
- ∀ Symptoms or signs consistent with COVID-19 infection (eg, fever, cough, dyspnoea), confirmed by an appropriate laboratory test.

Participants who meet criteria for bradycardia, orthostatic hypotension, who have had a syncope, or report anhidrosis or hypohidrosis should be evaluated by a cardiologist or neurologist as soon as possible.

Participants with AEs suggestive of new occurrence or worsening of peripheral neuropathy as per investigator's neurological assessment should be evaluated by a neurologist as soon as possible.

Participants with clinical signs/symptoms suggestive of worsening or new occurrence of heart failure should be evaluated by a cardiologist as soon as possible. Echocardiography should be performed if clinically indicated. The participant should not be dosed with the subsequent dose of IP until (if applicable) the absence of sensory abnormalities, sympathetic dysfunction, new occurrence or worsening of peripheral neuropathy or Class 3 or Class 4 (NYHA 1994) heart failure have been confirmed, or RPOA, SIF, primary osteonecrosis, or pathological fracture have been excluded.

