> 150 mmHg	≥ 30 mmHg systolic or ≥ 15 mmHg diastolic	 If either the 1 minute or 3 minute standing BP meets the orthostatic (postural) hypotension criteria, then the sequence is considered indicative of orthostatic hypotension. If 2 of 2 or 2 of 3 sequences are positive, then orthostatic hypotension is confirmed and an AE of orthostatic hypotension will be reported. 			

 Table 6
 Orthostatic Blood Pressure Criteria and Management

AE, adverse event; BP, blood pressure

Blood pressure changes meeting the prespecified criteria and confirmed as described above will be designated as a confirmed orthostatic hypotension episode. The event should be

reported as an AE whether or not the participant had accompanying symptoms. If a confirmed case of orthostatic hypotension occurs, the participant should be evaluated as soon as possible by a neurologist or cardiologist in order to determine the presence of sympathetic autonomic neuropathy. The participant should **not** receive further administration of IP until absence of sympathetic neuropathy is confirmed.

- ✓ If sympathetic neuropathy is confirmed, administration of IP will be permanently discontinued, and the participant will be asked to complete the assessments at the ET visit (Week 12 assessments) and then to enter the FU period (Section 7.1.2).
- ∀ If sympathetic neuropathy is not confirmed and orthostatic hypotension is not symptomatic, the participant can continue in the study as planned provided no more than 28 days passed since last IP administration (Section 7.1.3).
- ✓ If sympathetic neuropathy is not confirmed but orthostatic hypotension remains symptomatic for more than 14 days, administration of IP will be permanently discontinued, and the participant will be asked to complete the assessments at the ET visit (Week 12 assessments) and then to enter the FU period (Section 7.1.2).

Refer to the SoA (Table 1) for assessments to be performed at the ET visit and the FU period and Section 7.1.2 for procedures for early discontinuation of IP.

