8.3.4 Causality Collection

The investigator should assess causal relationship between IP and each AE, and answer 'yes' or 'no' to the question 'Do you consider that there is a reasonable possibility that the event may have been caused by the IP?'

For SAEs, causal relationship should also be assessed for other medication and study procedures. Note that for SAEs that could be associated with any study procedure, the causal relationship is implied as 'yes'.

A guide to the interpretation of the causality question is found in Appendix C.

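### Read as written, the first stopping criterion in Protocol 7.1.1 makes any drug-related AE a mandatory permanent stop, which leaves its own thresholds without effect and conflicts with 8.2.3.2 for related events

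*Protocol*

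**What the plan says.** Section 7.1 lists the situations in which IP is permanently discontinued. Two matter here. One leaves the decision to clinical judgement: "AE that, in the opinion of the investigator, contraindicates further dosing". Another imports the whole of the next subsection: "Development of any of the participant-specific criteria for discontinuation (Section 7.1.1").

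Section 7.1.1 then states that "further administration of IP will be stopped if any of the following scenarios occur". Its first scenario opens with "Reports of drug-related SAE(s) or drug-related AE(s) including but not necessarily limited to", followed by seven sub-bullets. Several carry a limit. Injection site reactions must be serious or severe. Sensory abnormalities must be at least moderate and persist beyond 14 days. A serious infection that is not systemic stops IP only if the investigator thinks it necessary.

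Section 8.3.4 has every AE rated yes or no on one question: "Do you consider that there is a reasonable possibility that the event may have been caused by the IP".

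Section 8.2.3.2 requires a confirmed episode of orthostatic hypotension to be "reported as an AE whether or not the participant had accompanying symptoms". It also says: "If sympathetic neuropathy is not confirmed and orthostatic hypotension is not symptomatic, the participant can continue in the study as planned", on condition that no more than 28 days have passed since the last dose.

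Section 7.1.3 offers a temporary hold for several event types, including "Participants who have the following sympathetic function AEs (any seriousness or severity"). It allows dosing to resume once the event has been judged not to meet the individual discontinuation criteria.

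**The concern.** The lead-in and the sub-bullets do different things. The sub-bullets read like thresholds, but the lead-in makes them examples of a wider class, and that class has no threshold. A mandatory permanent stop would then hang on a yes/no causality answer with a low bar.

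Two sites could apply the criterion differently to the same event, and the difference reaches the primary endpoint. Under Section 7.1.2, daily pain scores are not collected beyond the early termination visit. Under Section 9.4.2.1, data missing because of discontinuation for an AE are imputed as unfavourable, by a multiple imputation that returns the participant to baseline on average, and no retrieved-dropout data are collected. A participant who is still benefiting but is stopped for a mild related event would be analysed as a treatment failure.

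**Working it through.** No figure in the plan is at issue, so the check sets the rules side by side.

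**Step 1: is the first criterion a mandatory permanent stop?** The governing sentence in 7.1.1 is an instruction that applies if any one scenario occurs. Section 7.1, which covers permanent discontinuation, lists the 7.1.1 criteria as one of its grounds. So yes.

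**Step 2: do the sub-bullets limit the first criterion?** The lead-in says the list is not exhaustive, so an event that falls short of a sub-bullet is still a drug-related AE. The scenarios are alternatives, so a narrower criterion later in 7.1.1 does not switch off the first.

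**Step 3: compare outcomes for non-terminal cases, each rated related.**

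| Related event | First criterion of 7.1.1, literally | More specific rule |
|---|---|---|
| Mild injection site reaction | Stop | Sub-bullet asks for serious or severe |
| Mild, or quickly resolved, sensory abnormality | Stop | Sub-bullet asks for at least moderate and unresolved at 14 days |
| Serious non-systemic infection that the investigator thinks needs no stop | Stop | Sub-bullet leaves it to the investigator |
| Asymptomatic confirmed orthostatic hypotension, sympathetic neuropathy not confirmed | Stop | 8.2.3.2: can continue, within 28 days of the last dose |

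In the first three rows the limit does no work. In the fourth, two sections give opposite answers. If the orthostatic event is rated unrelated, there is no conflict.

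**Step 4: does another section reconcile the fourth row?** Section 8.2.2 has a parallel rule for reduced sweating, which lets the participant continue only if no other individual discontinuation criterion is met. Section 8.2.3.2 states only the 28-day condition and cites 7.1.3. If the deferral in 7.1.3 is read into 8.2.3.2, the result is that the continue rule is cancelled for every related case. That removes the rule rather than reconciling it.

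**Step 5: what is not a contradiction?** Section 7.1.3 defers to the discontinuation criteria, so it does not contradict 7.1.1; its resume rule simply has nothing left to act on for a held AE that is rated related. The liver rule in 8.2.11.1, which allows continuation with ALT or AST from 3 to below 5 times ULN, conflicts only if the rise is reported as an AE, which Section 8.3.7 restricts, and is also rated related.

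**Step 6: can the number affected be estimated?** Section 2.2.2 reports that in the ongoing Phase I volunteer study 2 of 5 treated participants (2/5 = 40.0%) had 4 TEAEs, all mild. Two of the four, injection site pain and paraesthesia, are of types for which 7.1.1 sets a higher bar. Relatedness and treatment assignment are not given, and the study is placebo-controlled. This shows that mild events of these types occur. It does not give a rate of extra stops.

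**The case against.** The strongest reply is that nobody would read the criterion literally, because the rest of the protocol assumes thresholds. Section 8.3.5 makes injection site reactions AESIs when they lead to permanent discontinuation, so some are expected not to. Section 8.2.9 grades these reactions as mild, moderate or severe. Section 8.3.3 records the action taken with IP separately from causality, and 8.3.7 mentions interruption as one such action. Section 7.1.1 has its own orthostatic criteria, which require sympathetic dysfunction on specialist evaluation or symptoms lasting more than 14 days. Appendix M shows that removing a renal-toxicity item from under this same lead-in was classed as substantial, which would make little sense if every related AE already stopped IP. The orthostatic conflict is also narrow, since it needs four conditions at once. And return-to-baseline imputation after an AE discontinuation is a deliberate part of the attributable estimand.

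Most of this stands as evidence of intent. It shows that the sponsor meant thresholds, and therefore that the binding sentence is misworded. It does not make that sentence say what was meant. The choice of estimand is not criticised here; the point is which participants the wording would send into it.

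Three stronger readings are tempting and are not supported. First, a reader might infer that the trial will lose participants or power: the documents give no rate of related mild AEs and do not show that any site applied the literal reading. Second, a reader might count several sections as contradicting 7.1.1: only 8.2.3.2 does so, and only for related events. Third, because serious systemic infection sits under the drug-related lead-in, a reader might infer that it should stop IP whatever its cause. That is a clinical preference. Section 7.1 already permits a stop for an AE that contraindicates dosing or for risk to the participant, and the Phase I participant with an unrelated serious pneumonia was in fact withdrawn (Section 2.2.2).

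**Conclusion.** The point holds as a drafting error in a mandatory rule. As written, any drug-related AE of any severity is a permanent stop, the limits in the sub-bullets have no effect, and there is one direct conflict, with 8.2.3.2, confined to events rated related. The conclusion rests on the ordinary meaning of the lead-in and on 7.1 making the 7.1.1 criteria permanent.

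The size is qualitative. A literal reading would move participants with mild related AEs into return-to-baseline imputation, and uneven readings across sites would make that depend on the site. The exposure is limited to the interval in which doses remain to be given, that is, up to the Week 10 dose. How many participants this touches cannot be derived from the documents. The wording should be corrected because the rule is binding and the correction is small; the point is not a challenge to the design or to the primary analysis.

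**What to change.** Replace the lead-in of the first criterion in 7.1.1 and keep the sub-bullets:

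*Any drug-related SAE (for serious non-systemic infection, as stated below); any of the following drug-related AEs at the threshold stated; or any other drug-related AE that in the investigator's opinion contraindicates further dosing (subject to Sections 7.1.3, 8.2.3.2 and 8.2.11.1):*

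Drug-related SAEs stay a mandatory stop, apart from the discretion already written for non-systemic infection. The thresholds for injection site reactions and sensory abnormalities take effect, and related but non-serious asymptomatic orthostatic hypotension follows 8.2.3.2. No change is proposed to the causality condition on serious systemic infection.

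The cost is one sentence in a protocol amendment, with no new visits, data or analyses. The one small downside is that a related, non-serious AE not on the list becomes a matter for the investigator, which Section 7.1 already provides for AEs.

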7.1.3 Temporary Discontinuation of Investigational Product

Withholding IP administration temporarily may be considered in the following cases:

- ∀ Development of sensory abnormalities (eg, paraesthesia, dysesthesia, burning, pins and needles) to confirm their resolution within 14 days prior to the next IP administration
- ∀ AE suggestive of new occurrence or worsening of peripheral neuropathy
- ∀ Participants who have the following sympathetic function AEs (any seriousness or severity):
 - # Meet the prespecified criteria for bradycardia (Section 8.2.4)
 - # Meet the prespecified criteria for confirmed orthostatic hypotension (Section 8.2.3.2)
 - # Have syncope
 - # Report anhidrosis or hypohidrosis
- ∀ Cases where additional evaluation or adjudication is needed to exclude possible or probable RPOA, SIF, primary osteonecrosis (including spontaneous osteonecrosis of the knee), or pathological fracture.

- ∀ Cases of signs/symptoms suggestive of worsening or new occurrence of heart failure
- ∀ When follow-up on cases of abnormal liver function is needed before the decision on permanent IP discontinuation is made (eg, identification of potential HL (PHL) cases needed or further evaluation in order to exclude HL required, or ALT or AST ≥ 5 × ULN for less than 2 weeks)
- \forall A positive test for SARS-CoV-2 at any time point during participation in the study.
- ∀ Symptoms or signs consistent with COVID-19 infection (eg, fever, cough, dyspnoea), confirmed by an appropriate laboratory test.

Participants who meet criteria for bradycardia, orthostatic hypotension, who have had a syncope, or report anhidrosis or hypohidrosis should be evaluated by a cardiologist or neurologist as soon as possible.

Participants with AEs suggestive of new occurrence or worsening of peripheral neuropathy as per investigator's neurological assessment should be evaluated by a neurologist as soon as possible.

Participants with clinical signs/symptoms suggestive of worsening or new occurrence of heart failure should be evaluated by a cardiologist as soon as possible. Echocardiography should be performed if clinically indicated. The participant should not be dosed with the subsequent dose of IP until (if applicable) the absence of sensory abnormalities, sympathetic dysfunction, new occurrence or worsening of peripheral neuropathy or Class 3 or Class 4 (NYHA 1994) heart failure have been confirmed, or RPOA, SIF, primary osteonecrosis, or pathological fracture have been excluded.

Please refer to the Appendix F for guidance on follow-up procedures for PHL and HL cases and Section 8.2.11.1 for management of other cases of abnormal liver function.

Administration of IP can be resumed if deemed appropriate by the investigator in participants with fully resolved asymptomatic or mild COVID-19 infection (confirmed by negative SARS-CoV-2 testing (ie, antigen-based), suggesting that the participant is no longer carrying replicating virus) provided that it is completely resolved without sequalae within 28 days since the previous IP administration and participants do not require ongoing treatment for COVID-19 infection as well as do not have ongoing adverse drug reactions associated with treatment of COVID-19 infection as assessed by the investigator. Additionally, more than 5 half-lives of COVID-19 antiviral medications should elapse before IP administration is resumed. Participants who were treated with anti-SARS-CoV-2 monoclonal antibodies are not eligible for further IP administration. For participants treated with COVID-19 antiviral medications, the investigator should contact the medical monitor and agree if and when further IP administration is appropriate.

If more than 28 days have elapsed since the last IP administration, IP should be permanently discontinued. The participants will be asked to complete the ET visit as soon as possible and then enter the FU period. Refer to the SoA (Table 1) for assessments to be performed at the ET visit and FU period and to Section 7.1.2 for procedures for early discontinuation of IP.

If less than 28 days have elapsed since the last IP administration and once the above mentioned events have been evaluated/adjudicated as not meeting individual discontinuation criteria (and the participant does not meet any other IP discontinuation criteria), IP should be administrated as soon as possible. The participant should be brought back to the study schedule as soon as feasible using the allowed visit windows (provided the interval between subsequent IP administrations is not shorter than 8 days).

7.1.4 **Procedures for Handling Incorrectly Enrolled or Randomised Subjects**

Participants who fail to meet the eligibility criteria should not, under any circumstances, be randomised or receive IP. Participants who are enrolled but subsequently found not to meet all the eligibility criteria must not be randomised and must be withdrawn (screen failed) from the study. A participant may be rescreened once and then be screen failed if he/she still does not meet the eligibility criteria (Section 5.4.1).

Where a participant does not meet all the eligibility criteria but is randomised in error, or incorrectly started on IP, the investigator should inform the sponsor's study physician or designee immediately.

